### **1.2 Blinding-single-blind**

Blind subjects: Patients were not informed of the specific anastomosis method, and postoperative care and follow-up procedures were kept consistent to avoid inter-group exposure differences.

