## **III. RESEARCH DESIGN**

### **1. Research on the overall design**

This prospective, single-blind, double-arm, multicenter, randomized controlled clinical trial with superiority design aims to compare postoperative intestinal function recovery between complete laparoscopic/robot-assisted right hemicolectomy combined with RISE anastomosis and traditional side-to-side anastomosis in patients with right-sided colon cancer. Eligible participants will be randomly assigned into RISE anastomosis and conventional anastomosis groups through zonal randomization, with evaluation of key outcomes including postoperative bowel function recovery (primary endpoint), complications, nutritional metabolism, quality of life, and oncological prognosis. Patients must provide informed consent prior to surgery, and all procedures are performed by senior physicians with extensive experience at each

center to ensure standardized protocols.

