### **1.1 Random grouping method-block randomization**

Randomized design: Block Randomization was used, and computer-generated random sequences (SAS 9.4) were used to assign subjects to either RISE or traditional groups on a 1:1 basis.

Group setting: The size of the fixed group is 4 cases (2 cases per group) to ensure balanced number of cases between groups. The order of the groups is randomly arranged (e.g., AABB, ABAB, BAAB, etc.) to prevent prediction of the distribution pattern.

Blind assignment: The random results are sealed in an opaque envelope, which only indicates the research center and the subject enrollment number. After signing the informed consent form, the independent research assistant of the sub-center unpacks the envelope to carry out the grouping, ensuring that the assignment process is irreversible and cannot be traced back.

Implementation process:

The random sequence is generated uniformly by the statisticians of the leading unit;

The groups were assigned according to the order of case reception in the sub-center;

If the number of cases in a sub-center is less than one group (4 cases), the remaining quota will be filled according to the random sequence.

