Figure 2 Schematic of RISE anastomosis steps. A-B: Identify and mark the transection sites on the transverse colon stump and terminal ileum. C-D: Evert the terminal ileum to mimic the anatomical structure of the ileocecal valve. E-F: Place fixation sutures at the transverse colon opening. G-H: Complete the RISE anastomosis of the terminal ileum with colon.

b. Conventional lateral side anastomosis group (control group)

After inserting the same cannula, ligating blood vessels, and making a 10 cm distal transection at the transverse colon mass along with a 15 cm proximal transection at the ileocecal valve, the specimen was extracted through a small midline incision. A linear stapler was used in vitro for the side-to-side ileocolonic anastomosis, followed by closure of the common intestinal incision with a second stapler. The anastomotic site was reinforced with 3-0 catgut sutures using reverse-staple technique.

(2) Intraoperative index recording:

- Total operation time (min);
- Surgical duration of anastomosis (min);
- Blood loss during operation (mL);
- Blood transfusion volume (mL);
- 

(3) Immediate postoperative monitoring:

- Blood pressure, heart rate, respiration and body temperature at 24h, 48h and 72h after surgery;
- Daily postoperative physical examination (abdominal signs, resumption of bowel sounds);
- Bristol stool score (recorded daily for 7 consecutive days);

(4) Laboratory test:

Blood routine and blood biochemistry (monitoring inflammatory indicators and metabolic status) at 24h and 72h after surgery;

(5) Postoperative complication records (according to Clavien-Dindo grading system):

Table 1. Clavien-Dindo grading system for surgical complications

I	
 
① Abnormal conditions that do not require medication or surgery, endoscopy and radiation therapy.
 
② Antispasmodic, antipyretic, analgesic, diuretic, electrolyte and other drug therapy and physical therapy.
 
③ Open infected wounds at the bedside
 

II	
 
① Complications requiring the use of medications other than those described above for treatment of grade I complications.
 
② Blood transfusion, total parenteral nutrition
 

III	Complications requiring surgery, endoscopy or radiation therapy
IIIa	No general anesthesia is required
IIIb	Need general anesthesia

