## **5. End-point indicators**

Key endpoint indicator: Time to first stool formation post-surgery (Bristol Stool Score <4): The Bristol Stool Scale categorizes stool into seven grades. As stool shape correlates with retention time in the colon, this score helps assess both intestinal transit time and anastomotic function. Scoring criteria: >5 indicates diarrhea, 6 represents mild diarrhea, and 7 signifies severe diarrhea. (Detailed scoring guidelines are provided in the appendix)

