## **3. Data management**

Use a unified EDC system (e.g., REDCap, Medidata) to set up logical checks (e.g., numerical ranges, required items).

Real-time monitoring of data entry progress and quality.

Data verification and cleanup:

Centralized data monitoring: periodic sampling of data and source documents (Source Data Verification, SDV).

Abnormal value automatic alarm (such as laboratory indicators beyond the normal range).

Central Laboratory and Imaging Center:

Biological samples are sent to the central laboratory for testing to avoid differences in testing between different laboratories.

The images were evaluated by an independent central laboratory in a blind manner.

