## ANNOTATIONS

Bristol defecation classification criteria

grade	expression
1	Hard small particles are difficult to pass and may be accompanied by constipation.
2	Irregularly shaped, chunky stools are difficult to pass and may be accompanied by constipation.
3	The stool is similar to a lump but smooth on the outside and easy to pass.
4	A banana-shaped stool is the standard form of normal bowel movements.
5	Soft and mushy stool, easy to pass, is a normal range of changes.
6	Fusel stools, relatively loose, may be accompanied by diarrhea.
7	Complete liquid stool is a sign of diarrhea.

Adverse event evaluation was based on the Clavien-Dindo complication scoring system.

TABLE 1. Classification of Surgical Complications

Grade	Definition
Grade I	Any deviation from the normal postoperative course without the need for pharmacological treatment or surgical, endoscopic, and radiological interventions Allowed therapeutic regimens are: drugs as antiemetics, antipyretics, analgetics, diuretics, electrolytes, and physiotherapy. This grade also includes wound infections opened at the bedside
Grade II	Requiring pharmacological treatment with drugs other than such allowed for grade I complications Blood transfusions and total parenteral nutrition are also included
Grade III	Requiring surgical, endoscopic or radiological intervention
Grade IIIa	Intervention not under general anesthesia
Grade IIIb	Intervention under general anesthesia
Grade IV	Life-threatening complication (including CNS complications)* requiring IC/ICU management
Grade IVa	Single organ dysfunction (including dialysis)
Grade IVb	Multiorgan dysfunction
Grade V	Death of a patient
Suffix "d"	If the patient suffers from a complication at the time of discharge (see examples in Table 2), the suffix "d" (for "disability") is added to the respective grade of complication. This label indicates the need for a follow-up to fully evaluate the complication.

\*Brain hemorrhage, ischemic stroke, subarachnoidal bleeding, but excluding transient ischemic attacks.  
CNS, central nervous system; IC, intermediate care; ICU, intensive care unit.

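### The protocol blinds only patients to the anastomosis and does not name a rater, blinded or otherwise, for the Bristol grade that defines the primary endpoint

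*Protocol*

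**What the plan says.** The overall design section (III.1) labels the trial: "This prospective, single-blind, double-arm, multicenter, randomized controlled clinical trial with superiority design". Section III.1.2 says what single-blind means here: "Blind subjects: Patients were not informed of the specific anastomosis method, and postoperative care and follow-up procedures were kept consistent". The second half of that sentence concerns uniform care and follow-up. Ward staff, outcome assessors and analysts are not mentioned.

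The primary endpoint in section III.5 is "Time to first stool formation post-surgery (Bristol Stool Score <4" on the seven-grade scale. The data come from the treatment-period list in section III.4, under immediate postoperative monitoring: "Bristol stool score (recorded daily for 7 consecutive days". Neither place names a rater.

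Two other places bear on the question. Section V.3 provides masked assessment for one kind of data: "The images were evaluated by an independent central laboratory in a blind manner". Section III.1.1 describes who learns the allocation: "the independent research assistant of the sub-center unpacks the envelope to carry out the grouping". That assistant is called independent, but nothing bars the assistant from later rating outcomes.

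**The concern.** A Bristol grade is assigned by matching a stool to a short verbal description. The primary event turns on the boundary between grades 3 and 4. The annex describes grade 3 as lump-like with a smooth surface, and grade 4 thus: "A banana-shaped stool is the standard form of normal bowel movements". Two careful raters can differ on a stool near that line.

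The endpoint is the first qualifying stool, so one generous rating is enough to fix the event time for that patient. The expectation also has a direction: the research context section already reports a gate effect and better bowel function with RISE. A rater who knows the arm and shares that expectation could resolve borderline stools in favour of RISE. Once the grades are recorded, no analysis can separate such a shift from a treatment effect.

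Surgeons cannot be blinded to the anastomosis they perform. The person who grades the stool can be, so the gap is avoidable.

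**Working it through.** **1. What the text settles and what it leaves open**

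| Question | Answer in the protocol | Place |
|---|---|---|
| Who is blinded to the anastomosis? | Patients | III.1, III.1.2 |
| What decides the primary endpoint? | First stool with Bristol grade below 4 | III.5 |
| How often is it graded? | Daily for 7 days after surgery | III.4, treatment period |
| Who assigns the grade? | Not stated | – |
| Must that person be unaware of the arm? | Not stated | – |
| Is any outcome read blind? | Yes, images, by a central laboratory | V.3 |

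The defect is therefore that the rater and the rater's blinding status are not specified. The protocol contains no figure on this point to reproduce.

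**2. Illustration of the size**

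Inputs from the sample size section (III.3): 33.3% formed on day 2 in the control arm, 85 patients per arm, two-sided alpha 0.05. One input is assumed and has no basis in the documents: a share f of unformed RISE patients rated as formed, with no misrating in controls. The share f is applied once per patient.

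Under no true effect, the apparent RISE proportion is p = 0.333 + f × (1 − 0.333) = 0.333 + 0.667f:

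- f = 0.05: 0.333 + 0.033 = 0.366
- f = 0.10: 0.333 + 0.067 = 0.400
- f = 0.20: 0.333 + 0.133 = 0.466

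The chance of P < 0.05 comes from the pooled two-proportion z-test. It was computed exactly by summing the two binomial distributions (85 and 85) over all results with |z| > 1.96, and checked by the normal approximation Φ((d − 1.96·s0)/s1) + Φ((−d − 1.96·s0)/s1). Here d = p − 0.333, s0 is the pooled and s1 the unpooled standard error.

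Worked for f = 0.10: d = 0.0667; pooled proportion 0.366; s0 = √(2 × 0.366 × 0.634 / 85) = 0.0739; s1 = √((0.400 × 0.600 + 0.333 × 0.667)/85) = 0.0737. The first term is Φ((0.0667 − 0.1449)/0.0737) = 0.145 and the second is 0.002, which gives 0.147.

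| Share f misrated | Apparent RISE rate | Exact | Normal approximation |
|---|---|---|---|
| 0 | 33.3% | 4.9% | 5.0% |
| 5% | 36.6% | 7.2% | 7.4% |
| 10% | 40.0% | 14.4% | 14.7% |
| 20% | 46.6% | 43.0% | 42.6% |

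At f = 0.10, 14.2 of the 14.4 percentage points are rejections in favour of RISE.

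**3. Limits of the illustration**

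The endpoint is a time to first formed stool, not a day-2 proportion. The day-2 proportion is used because the protocol bases its own sample size on it. With several stools per patient, misrating per stool would accumulate differently. The table shows how sensitive the comparison is to one-sided rating. It does not estimate what will happen.

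**The case against.** The strongest reply is that the protocol is silent, and silence is not unblinded rating. A reader might infer from the score's place beside vital signs and the daily physical examination that ward staff who know the operation do the grading and that the patient does not. The text does not support that: a list heading assigns no rater. Some of it points towards patient-sourced grading. The annexed scale defines grades 1, 2, 3 and 5 partly by how easily the stool passes, which normally comes from the patient. The schedule also asks for a Bristol score at screening and at 1, 3, 6 and 12 months, when ward staff would not usually see the stool. This stands. It rules out stating that unblinded staff rate the outcome, but it does not establish that patients do.

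A second reply is that sections V.1 to V.4 provide a unified operation manual, assessed training, source data verification and closer monitoring of primary endpoints. These help consistency, and the manual might name the rater. None of them keeps the rater unaware of the arm.

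A third reply is that the statistical analysis plan may cover the point. Who rates and who is blinded is trial conduct, which belongs in the protocol, and an analysis cannot undo rating bias.

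A fourth reply is that the misrating shares are invented and run one way in one arm. That is correct, and the figures are offered only on those terms.

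**Conclusion.** The concern holds in a limited form. The protocol blinds only patients to the anastomosis, names no rater for the grade behind its primary endpoint, and does not require that rater to be unaware of the arm. It does specify blinded reading for images. Following the plan as written therefore permits biased ascertainment of the primary outcome.

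This can bias the comparison; the documents do not show that it will. Bias would require a rater who knows the arm and leans towards RISE, and neither is established. If blinded patients already grade their own stools, the risk is smaller and one sentence closes the gap.

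The size is illustrative only: a false-positive rate of about 7%, 14% or 43% if 5%, 10% or 20% of unformed RISE patients were rated as formed. This assumes no true effect, no misrating in controls, and a day-2 two-proportion test standing in for the time-to-event endpoint. The point should be corrected before data are collected.

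**What to change.** State in section III.1.2, and again beside the Bristol item in the treatment-period list of section III.4, that the grade used for the primary endpoint is assigned by someone unaware of the arm. Either of two sources would do:

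- the blinded patient, using the annexed scale (a text table in the document at hand); or
- existing ward staff who took no part in the surgery or in opening the envelope.

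Keep the anastomosis type off the stool record sheet. Name the chosen source as the source of the primary endpoint and use the same one at all five centers.

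The cost is a record sheet and a training line in the SOP, with no extra assessor or procedure. Self-scoring adds some rating noise. It also relies on patient blinding holding: the control arm has a midline extraction incision, while the RISE extraction site is not described, so equal noise in the two arms should not be taken for granted.

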## **2. Selection and withdrawal of participants**

**Research site: General Surgery, Second Affiliated Hospital of Army Medical University**

Patients who meet the diagnostic criteria for right-sided colon cancer in the

NCCN Colon Cancer Guidelines and are candidates for radical surgical resection.

**Inclusion criteria:**

- a. The study was conducted with subjects aged 18 to 80;
- b. ASA score is less than 3 points;
- c. Patients with a first diagnosis of tumor located in the appendix, ileocecal region, ascending colon, hepatic flexure of colon and right 1/3 of transverse colon, or patients who plan to undergo laparoscopic radical resection of the right half of colon;
- d. No other history of digestive tract disease (except intestinal polyps and gallstones)
- e. Willing to participate in this study and sign the informed consent form;
- f. Clinical data is complete.

**Exclusion criteria:**

- a. Patients with other malignant tumors of organs;
- b. Tumors invade local surrounding organs;
- c. Patients with other infectious or autoimmune diseases (e.g., Crohn's disease);
- d. Patients have congenital or acquired metabolic diseases;
- e. Have taken antibiotics and other drugs that interfere with the flora within one month before being selected for research;
- f. The plan of the operation was changed, and the resection did not include the ileocecal valve;

**Exit criteria:**

- a. Subjective withdrawal: the patient explicitly refuses to continue to participate in the study or adopts the anastomosis method of reconstructing the ileocecal valve.
- b. Withdrawal by the investigator:
  - During or after the operation, complicated conditions (such as severe abdominal adhesion, more difficult than expected) are found, which make it impossible to complete the operation according to the established plan.
  - The patient's postoperative condition changes (such as severe complications, infection, etc.) are not suitable for continued participation in the study after evaluation by the investigator.
- c. Missing follow-up: the patient is unable to complete the follow-up (e.g., lost

contact, refusal to further examination).

d. Protocol deviation: the subject did not receive the intervention or follow-up as required by the study protocol, affecting the validity of the data.

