treating children with congenital ileocecal valve atresia and patients requiring combined resection due to non-neoplastic causes [9], indicating potential clinical benefits of ileocecal valve reconstruction. However, these approaches also present notable limitations: (1) The relatively thin colon wall makes submucosal tunnel reconstruction prone to bowel perforation; (2) The complex procedural steps hinder clinical application and promotion.

Building on these findings, this study proposes an innovative ileocolonic anastomosis approach based on the integrated reconstruction concept of mucosal folds within the ileocecal valve and the annular muscle outside the valve. The "Revolute Insert Side-End ileocecal valve reconstruction (RISE)" method combines "revolute insertion of the ileocecal valve" with "sleeve embedding reconstruction of the colonic muscle" in the ileal pouch. Preliminary small-sample clinical data demonstrate that this RISE-based ileocecal valve reconstruction technique features simple operation and a distinct "gate effect". Compared to conventional ileocolonic side-to-side anastomosis, patients with RISE anastomosis exhibit faster postoperative intestinal function recovery and significantly improved bowel function quality, highlighting the unique advantages of RISE. Notably, there was no significant difference in short-term complications between RISE and conventional anastomosis groups, indicating good surgical safety. This study plans to conduct a multicenter clinical comparative trial combining complete laparoscopic/robot-assisted right hemicolectomy with RISE anastomosis, observing its effects on short-term and long-term complication rates, quality of life, bowel function, gut microbiota, nutrient absorption, and long-term oncological outcomes.

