### **3. Sample size:**

This prospective, double-arm, single-blind, multicenter randomized controlled trial evaluated the effectiveness of RISE anastomosis with ileocecal valve reconstruction. The postoperative stool formation time served as the primary endpoint for sample size calculation. Based on our prior trial results, the stool formation rate was approximately 65% in the RISE group and 33.3% in the control group on day 2 postoperatively. With a two-tailed test level  $\alpha=0.05$  and a 1:1 group ratio, PASS11.0 software estimated minimum sample sizes of 85 cases per group. Considering a 10% dropout rate, each group required 94 additional cases ( $85 + 85 \times 10\%$ ), totaling 188 cases combined. The study employed block randomization with minimum blocks of 4 samples. Subsequently, sample allocation was determined based on regional average patient intake levels to match block sizes.

According to the number of patients with right-sided colon cancer admitted by each center per year, the number of cases was allocated proportionally among the research centers,

Table 1 Sample size allocation of each sub-center

Center units	Sample size allocation
Second Affiliated Hospital of Army Military Medical University	108
The First Affiliated Hospital of Chongqing Medical University	20
Affiliated Hospital of North Sichuan Medical College	20
Guangan People's Hospital, Sichuan Province	20
Third People's Hospital of Yibin City, Sichuan Province	20

[figure not shown]

Figure 1 PASS11.0 software interface-sample size calculation results

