## 2. Treatment

Time node: from intraoperative to 7 days after surgery

Research content and items to be collected/detected:

(1) Operation implementation:

In this study, the intervention group and the control group only differ in the digestive tract reconstruction method:

a. RISE anastomosis group (intervention group)

All procedures were performed under general anesthesia with the patient in lithotomy position. In accordance with established principles of laparoscopic right hemicolectomy, five cannulation needles were inserted to facilitate D2 lymph node dissection from inside out.

Step 1: Measurement and Dissection: Mark a 2 cm mark along the mesocolon at the terminal transverse colon, and mark the ileal distal end approximately 10 cm and 12 cm from the ileocecal junction. Use an endoscopic linear stapler to dissect the right half of the transverse colon. Perform mesenteric trimming on the ileal distal segment, ligate the ileum at marked points with 4-0 silk sutures, then dissect it using an ultrasonic scalpel. Carefully inspect both ends and disinfect with alcohol swabs.

Step 2: Intestinal End Inversion and Colon Insertion: Using an ultrasonic scalpel, make a horizontal incision 2 cm from the colon's distal end. Divide the proximal ileum into three equal segments, then suture them to the muscularis **浆膜** layer with 3-0 silk sutures, creating a 1.5 cm mucosal flap to form a simulated ileocecal valve. Perform an interrupted suture of three stitches at the midpoint of the inverted ileal segment using 3-0 silk sutures. Insert the intact ileal segment into the colon without

torsion, ensuring adjacent mesenteric vessels are free from torsion and tension.

**Step 3: Intestinal Colon End-to-End Anastomosis.** When there is no intestinal volvulus, fix three sutures at the transverse colon opening, one-third of the distance from the mid-point of the small bowel eversion line, to ensure precise fixation of the small intestine on the transverse colon. Close the anastomosis with 3-0 catgut suture (with barbs) using a tight stitch. If the closure is inadequate, perform interrupted suturing. After confirming no significant fistula formation, encase the anastomosis with seromuscular layer. Continuously suture the gap between the ileum and colonic mesentery with 3-0 catgut suture (with barbs). Finally, manually assess the anastomosis's size and patency.

[figure not shown]

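### Exit criterion a names the valve-reconstructing anastomosis, which is the trial's own intervention, as a ground for withdrawal; on any plausible reading that limb is either tied to one arm or redundant

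*Protocol*

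**What the plan says.** Exit criterion a (Protocol, III.2, Exit criteria) has two limbs. The first is "Subjective withdrawal: the patient explicitly refuses to continue to participate in the study". The second follows directly: "or adopts the anastomosis method of reconstructing the ileocecal valve". The grammatical subject of both is the patient.

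Other sections fix what that method is and who chooses it:

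- The research context names the intervention "Revolute Insert Side-End ileocecal valve reconstruction (RISE" (the abbreviation closes the bracket). The sample size section says that the trial "evaluated the effectiveness of RISE anastomosis with ileocecal valve reconstruction".
- The control arm has no valve reconstruction: "A linear stapler was used in vitro for the side-to-side ileocolonic anastomosis" (Treatment, control group).
- The arm is set by a sealed envelope: "After signing the informed consent form, the independent research assistant of the sub-center unpacks the envelope" (section 1.1).
- The RISE description states "All procedures were performed under general anesthesia" (Treatment).
- On blinding, section 1.2 states "Patients were not informed of the specific anastomosis method".

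The data management and statistical analysis section places lost cases in the intention-to-treat analysis, with imputation of missing data. It gives no rule for patients who exit under criterion a.

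**The concern.** An exit criterion is an operative rule that sites apply to individual patients. This one refers to the treatment under test. A site that follows it must guess the meaning, and two of the plausible meanings remove patients from one arm because of the anastomosis they were allocated or received.

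At stake is the randomised comparison. If exits depend on treatment and occur in one arm, and if those patients are then left out, the comparison moves towards an as-treated one. Timing matters too: the stool score is recorded daily for seven days after surgery, and if a patient is exited within that week and recording stops, no later analysis plan can recover the primary outcome. The limb also presumes that a patient knows or chooses a method that the blinding section withholds.

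**Working it through.** **Readings of the second limb, set against the other sections**

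1. *Literal: the patient adopts the reconstruction.* Every RISE patient treated as allocated meets the criterion (up to 94 of 94), and no control patient treated as allocated does. No site would apply it this way, so the figure describes the wording and not a likely effect.
2. *Refuses to adopt the allocated reconstruction.* Only a patient allocated to RISE can meet it. It also requires the patient to know the allocation, which section 1.2 withholds.
3. *A control patient receives the reconstruction.* Only control patients can meet it. It is then a crossover decided in theatre, not a subjective act of the patient, so it is filed in the wrong place.
4. *A still-blinded patient objects to reconstruction in general.* This can happen in either arm with the blind intact. It amounts to refusing to continue, which the first limb covers.

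Readings 1 to 3 act on one arm. Reading 4 makes the limb redundant. None gives it a legitimate function that the first limb lacks.

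**The plan's own figures (background)**

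The dropout step reproduces: 85 × 1.10 = 93.5, rounded to 94 per group, and 2 × 94 = 188. The allowance is 94 − 85 = 9 patients per arm.

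**Illustration of size under reading 2**

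The documents give no exit rate, so the share *w* of RISE patients who exit is assumed. At 5%, 0.05 × 94 = 4.7 patients; at 10%, 0.10 × 94 = 9.4 patients. That is about half, or all, of the allowance of 9, in one arm.

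*Power.* With the planning rates of 65% and 33.3%, a two-sided 5% level and exits at random in the RISE arm only, power is 99.4% with no exits, 99.2% at *w* = 10% and 98.8% at *w* = 20%. Loss of power is not the issue.

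*Bias, worst case.* Assume that the true day-2 rate is 33.3% in both arms, that exits occur only in the RISE arm, that none of those patients had formed stool by day 2, and that all are dropped from the analysis. Then:

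- observed RISE rate p₁ = 0.333 / (1 − w), with n₁ = 94(1 − w)
- SE = √[p₁(1 − p₁)/n₁ + 0.333 × 0.667/94]
- δ = p₁ − 0.333
- two-sided rejection rate = 1 − Φ(1.96 − δ/SE) + Φ(−1.96 − δ/SE)

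| w | n₁ | p₁ | rejection rate (nominal 5%) |
|---|---|---|---|
| 5% | 89.3 | 35.1% | 5.7% |
| 10% | 84.6 | 37.0% | 8.1% |
| 20% | 75.2 | 41.6% | 20.0% |

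The shift favours RISE. It uses the day-2 proportion on which the sample size rests, as a simple stand-in for the time-to-formation endpoint.

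**The case against.** The strongest reply is that this is a wording slip in a visibly translated text. The heading is subjective withdrawal and the verb in the first limb is to refuse, so the natural sense is refusing to continue or to adopt the reconstruction. Read so, it records a patient's right to decline, which the ethics section protects. This stands as an explanation of how the sentence arose. It does not make the sentence usable, because the repaired version is either selective or redundant.

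Three stronger readings are tempting, and the documents do not support them:

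- *A reader might infer that the limb acts on one arm under every reading, or works only once the blind is broken.* Consent precedes the envelope, the study procedures are explained beforehand, and section 1.2 withholds the specific method without saying that patients are unaware reconstruction is possible. A consented, blinded patient in either arm could object to it in general. What patients are told about the two methods cannot be checked, because the consent pages are not in the reviewed copy.
- *A reader might infer that the whole RISE arm would be withdrawn.* That follows only from the literal wording, which no site would apply.
- *A reader might infer that the primary result will be biased.* The exit criteria do not say that exited patients leave the analysis. The intention-to-treat sentence may have been meant to cover them, and analysis sets are commonly defined in the statistical analysis plan, which is not at hand.

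It is also fair to say that removing this limb alone would not keep crossovers in the study. Criterion b (first bullet) exits patients whose operation cannot be completed as planned, and criterion d exits those not treated or followed as the protocol requires. The fix must deal with both.

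**Conclusion.** The point holds as an error in an operative rule. The second limb of exit criterion a makes the trial's own intervention a withdrawal ground. Its plausible meanings are selective by arm or add nothing, and applied to the allocated method it conflicts with patient blinding. This conclusion rests on the text alone.

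The effect on the result is a risk of unknown size, not a demonstrated bias. It depends on how sites read the limb, how many patients exit, whether their stool scores continue, and whether they stay in the analysis. The 5 to 10% exit rate is an assumption. The rejection rates of 5.7% and 8.1% at those shares (20.0% at 20% exits) need every exit to be in the RISE arm, without formed stool by day 2, and dropped. They show direction and an upper range, not an expected value. The correction is still worth making because it loses nothing legitimate and cannot be made once patients have been exited.

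**What to change.** 1. Delete the second limb of exit criterion a, leaving the patient's own refusal to continue in the study.
2. State that a patient who receives an anastomosis other than the one allocated, in either direction, stays in follow-up and in the allocated arm for the intention-to-treat analysis. The daily stool scores and all visits continue, and the anastomosis performed and the reason are recorded.
3. Reconcile exit criteria b (first bullet) and d with this statement, so that they do not remove the same patients by another route.
4. Extend the intention-to-treat sentence in the data management and statistical analysis section beyond lost cases, so that the analysis status of every exited patient is clear.

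The cost is a few sentences across these sections and one or two case report form fields. The statistical price is dilution by retained crossovers. If a share *c* of one arm receives the other method and takes on that arm's rate, the planned difference of 65 − 33.3 = 31.7 percentage points becomes 31.7 × (1 − c): 30.1 points at an assumed 5%, and 28.5 at 10%.
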